2.4 BASELINE EVALUATION

HISTORY AND PHYSICAL EXAMINATION

- Medication review
- Directed physical examination, including body mass index calculation
- Detailed skin examination including:
 - Total body surface area involvement (TBSAI)
 - Physician global assessment (PGA)
 - Pustular psoriasis assessment severity index (PPASI)
 - Palmoplantar psoriasis assessment severity index (PPPASI), if appropriate

BLOOD AND TISSUE

- Complete blood count with differential
- Serum creatinine and urea nitrogen
- Serum calcium, phosphorus
- Parathyroid hormone
- Serum 25-OH Vitamin D
- Hepatic panel including alkaline phosphatase
- Serum albumin and total protein
- Lipid Panel (total cholesterol, triglycerides, LDL, HDL)
- Serum insulin level

Abbreviated Title: Anakinra in pustular dermatoses

Version Date: December 12, 2018

- Serum C-peptide
- Acute phase reactants: erythrocyte sedimentation rate, serum high-sensitivity C-reactive protein
- Serum ferritin
- Serologies: anti-nuclear antibody, anti-dsDNA antibodies, anti-ENA antibodies, rheumatoid factor, C3, C4, CH50.
- Quantitative serum immunoglobulins
- HLA class I and II typing
- Serum protein electrophoresis
- Anti-streptolysin O titer
- Viral Markers Hepatitis Screen (HbsAg, Anti-HCV)
- Skin biopsies: up to 3 (lesional x2, and non-lesional skin x1) (performed at the investigator's discretion)
- Serum, plasma and tissue cytokine levels
- Serum beta human chorionic gonadotropin (not required if females are status post hysterectomy or postmenopausal)
- Serum glucose
- Serum storage for research

URINE

- Urine protein electrophoresis
- Urinalysis
- Urine calcium, phosphorus

QUESTIONNAIRES/MEASUREMENTS

- Quality of life assessments/questionnaires including DLQI, SF-36, Pruritus VAS, Pain VAS, and Overall Disease Severity VAS (details in Section 3.4)
- Total body photography (performed at the investigator's discretion)

CONSULTATIONS

The following consultations will be conducted at the investigator's discretion:

- Rheumatologic consultation including baseline joint examination with assessment by ACR criteria, including Health Assessment Questionnaire
- Cardiometabolic evaluation including baseline electrocardiogram
- Ophthalmologic examination
- Gastrointestinal consultation when indicated

RADIOLOGICAL

The following procedures will be conducted at the investigator's discretion:

- Total body research FDG-PET CT scan
- Joint MRI of affected joints

Abbreviated Title: Anakinra in pustular dermatoses

Version Date: December 12, 2018

3 STUDY IMPLEMENTATION

3.1 STUDY DESIGN

This will be a phase 2, open label, prospective interventional 16-week dose titration study. Patients will complete a daily diary during the entire 16-week study course. Patients will be instructed to score the severity of rash, pustules, itch, skin pain, joint pain and overall well-being into their daily diaries. They will also document fever and doses of medications in their diaries.

(APPENDIX B: PATIENT)

At the baseline visit, clinical assessments, and laboratory, histopathologic and subjective data will be collected. All enrolled patients will initially receive treatment with anakinra 100 mg/day via self-administered subcutaneous injection. The first dose of anakinra will be administered under supervision in the clinic.

At week 4, disease response will be assessed by clinical exam, laboratory markers and evaluation of patient diaries that are returned to clinic. Determination for dose escalation will be made based on week 4 assessments. Those patients who do not achieve complete disease clearance with initial anakinra dosing will be increased to the next incremental dose level (see Section 3.1.2).

At week 8, patients will return for clinical evaluation and patients who do not achieve complete disease clearance on anakinra have the option of dose escalation up to the next incremental dose level. All patients will stop anakinra at week 12.

Patients will return for an Off Study visit at week 16, approximately 28 days after their final dose is administered. Considering personal/work/travel/other obligations, a period of no more than 1 week before or after the Week 4, 8, or 12 visits, and 2 weeks before or after the Week 16 visit may be permitted.

Total body photographs will be taken at baseline, week 4, week 8, week 12 and week 16 (at the investigator's discretion).

With the patient's consent, and at the discretion of the investigator, a skin biopsy for research will be taken at baseline and week 12. Skin biopsies will be taken from lesional and non-lesional skin. Non-lesional skin will be obtained for the purpose of comparison with lesional skin in immunohistochemistry, cytokine and gene expression studies, as well as in vitro keratinocytes studies.

3.1.1 Dose Limiting Toxicity

All patients will be evaluable for toxicity from the time of their first treatment with anakinra until the end of study participation, regardless of inclusion in primary response evaluation.

This study will utilize version 4.0 of the NCI Common Terminology Criteria for Adverse Events (CTCAE) (<http://ctep.cancer.gov/reporting/ctc.html>) for toxicity and adverse event reporting. Only those adverse events deemed possibly, probably, or definitely related to anakinra will be used in the definition of dose-limiting toxicity. Greater or equal to CTCAE grade 3 toxicity in any enrolled subject thought to be possibly, probably or definitely associated with anakinra will be reported to the IRB. The adverse event will be presented to the IRB and safety monitor for review and consideration of protocol modification including possible trial termination. Events that are considered disease-related will not be considered dose limiting or medication-induced adverse events.

3.1.2 Dose Escalation

An initial dose of anakinra 100 mg/day will be administered daily via self-administered subcutaneous injection. If pustule formation persists at this dose, anakinra dose may be escalated up to 200 mg/day injected subcutaneously daily at week 4. Participants will be re-assessed at week 8, and if pustule formation persists and the patient weighs ≥ 75 kg, the dose may be escalated up to a maximum 300 mg/day.

Dose Escalation Schedule	
Dose Level	Dose of anakinra
Level -1*	50mg SC daily
Level 1	100 mg SC daily
Level 2	200 mg SC daily
Level 3	300 mg SC daily (patients ≥ 75 kg only)

Abbreviated Title: Anakinra in pustular dermatoses

Version Date: December 12, 2018

*Patients who experience an adverse event on dose level 1 that requires dose reduction may be reduced to dose level -1, 50mg SC daily (see Section 3.3). Patients who require dose reduction due to an adverse event at any point in this study will not be eligible for dose escalation.

Dose escalation will follow the rules outlined in the Table below.

Time of Assessment	Escalation Decision Rule
Baseline	
 Enter each patient onto study at dose level 1
Week 4	
 If patient has achieved complete clearance of pustular and plaque disease, remain at dose level 1 If patient has not achieved complete pustule and plaque clearance, increase to next incremental dose level
Week 8	
 If patient has achieved complete clearance of pustular and plaque disease, remain at current dose level If patient has not achieved complete clearance of pustular and plaque disease AND patient weighs ≥ 75kg, increase to next incremental dose level

If a patient experiences a Grade 2 adverse event probably or definitely related to anakinra within 7 days prior to a scheduled dose escalation, dose escalation will be postponed until resolution of the adverse event or a maximum of 14 days, whichever is shorter.

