3.2 DRUG ADMINISTRATION

Anakinra is supplied in single-use 1 ml prefilled glass syringes with 27 gauge needles as a sterile, clear, colorless-to-white, preservative-free solution for daily subcutaneous (SC) administration. Each 1 ml prefilled glass syringe contains: 0.67 ml (100 mg) of anakinra in a solution (pH 6.5) containing sodium citrate (1.29 mg), sodium chloride (5.48 mg), disodium EDTA (0.12 mg), and polysorbate 80 (0.70 mg) in water for injection, USP.

Patients will be instructed verbally and in writing that anakinra should be protected from light, stored in the refrigerator at 2°C to 8°C (36°F to 46°F) away from children, and never frozen. Patients will be instructed not to use any syringe if the solution appears discolored or cloudy or has been at room temperature ≥ 24 hours. Patients will be instructed to avoid shaking the pre-filled syringes, to use each syringe only once, and to inject the entire volume of solution. Patients will receive a diagram (**APPENDIX C: PATIENT HANDOUT**) of body sites where anakinra is to be injected, emphasizing the importance of avoiding veins, arteries and injecting into a new site each day. Self-injection demonstration and technique will be provided once the baseline visit has concluded.

All patients will be given a puncture-resistant container for proper disposal of syringes after use.

Abbreviated Title: Anakinra in pustular dermatoses

Version Date: December 12, 2018

All patients will initiate anakinra therapy with one 1ml (100 mg) prefilled syringe injected subcutaneously daily. Those who achieve disease quiescence on this dose by week 4 will continue at this dose until week 12.

Those who do not demonstrate disease quiescence at week 4 will increase their dose to 2-1ml prefilled syringes (total of 200 mg) to be injected subcutaneously daily. Those individuals who weight >75kg and do not demonstrate disease quiescence by week 8 on anakinra 200 mg/day will be instructed to increase their dose to 3-1ml prefilled syringes (total of 300mg) injected subcutaneously daily.

Patients who miss a dose will be instructed to administer the dose as soon as they remember. However, if it is almost time to administer the next dose, the patient will be directed to skip the missed dose and proceed with their regularly scheduled dose. Patients will be reminded to avoid double-dosing in an effort to make up the missed dose.

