Research blood sampling		X						X		
Rheumatology Consultation including ACR assessment ^e		X		X		X		X		X
Cardiometabolic evaluation including electrocardiogram		X						X		
Ophthalmologic examination		X						X		
Gastrointestinal consultation		X						X		

Abbreviated Title: Anakinra in pustular dermatoses

Version Date: December 12, 2018

	Screening ≤8 weeks prior to enrollment	Baseline- up to drug initiation ^a	Weeks 1, 2, 3 (+/- 3 days)	Week 4 (+/- 1 week)	Weeks 5, 6, 7 (+/- 3 days)	Week 8 (+/- 1 week)	Weeks 9, 10, 11 (+/- 3 days)	Week 12 (+/- 1 week): End of Treatment	Weeks 13, 14, 15 (+/- 3 days)	Week 16 (+/- 2 weeks): Post Therapy Follow- up ^a
QOL/questionnaires ^f		X		X		X		X		X
Daily scoring diary		Start Day 0		X-----X						
AE Monitoring		START	X	X	X	X	X	X	X	X

^a Additional clinical labs may be obtained as indicated at baseline and follow up visits

^b As indicated in section 10.3, all subjects at NIH will be offered the opportunity to complete an NIH advanced directives form. This should be done preferably at baseline but can be done at any time during the study as long as the capacity to do so is retained. The completion of the form is strongly recommended, but is not required.

^c If escalation criteria are met (see Section 3.2)

^d Within 8 weeks of enrollment

^e If the rheumatology consult is done at Week 0, the patient will be seen again at Week 12. If there is evidence of joint disease, patients will be strongly encouraged to have rheumatology consult during all clinic visits (Weeks 0, 4, 8, 12 and 16)

^f QOL/questionnaires (see Section 3.4)

^g Skin biopsy for hematoxylin and eosin staining to confirm diagnosis if prior confirmational biopsy has not been performed

^h Performed at the investigator's discretion for research purposes

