6.2.2 Disease Parameters

Measurable disease: Total body surface area involvement of pustules and erythematous plaques will be measured in this study. At the time of enrollment, all study participants will have active disease warranting systemic therapy, as defined by macroscopic non-infective pustular and inflammatory skin lesions involving $\geq 5\%$ of the total body surface area, or palmoplantar involvement.

Joint involvement will also be assessed using criteria set forth by the American College of Rheumatology.

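### Sections 3.1, 3.1.2 and 3.2 give conflicting week-8 dosing rules; for one type of patient no dose satisfies both the escalation table and Section 3.2

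*Combined protocol and SAP*

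**What the plan says.** Four pieces of current text govern the dose from week 8.

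- **Section 3.1.** At week 8, "patients who do not achieve complete disease clearance on anakinra have the option of dose escalation up to the next incremental dose level". The sentence has no weight condition. The week-4 sentence in the same section is a directive and refers to Section 3.1.2 for the dose levels.
- **Section 3.1.2, text.** The trigger is persisting pustules and the wording is permissive: "If pustule formation persists at this dose, anakinra dose may be escalated up to 200 mg/day injected subcutaneously daily at week 4". The week-8 sentence is also permissive, for patients of at least 75 kg, up to a maximum of 300 mg/day.
- **Section 3.1.2, table.** It is introduced by "Dose escalation will follow the rules outlined in the Table below". A patient clear of pustules and plaques at week 8 stays at the current level. "If patient has not achieved complete clearance of pustular and plaque disease AND patient weighs" at least 75 kg, the instruction is to go up one level, whatever the current level.
- **Section 3.2.** Patients on 100 mg/day: "Those who achieve disease quiescence on this dose by week 4 will continue at this dose until week 12". Its only week-8 step is for patients already on 200 mg/day: "Those individuals who weight >75kg and do not demonstrate disease quiescence by week 8 on anakinra 200 mg/day will be instructed to increase" to 300 mg/day.

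The Study Calendar (Section 3.6) marks dose titration at weeks 4 and 8. Its footnote c reads "If escalation criteria are met (see Section 3.2"), so it points to Drug Administration and not to the table.

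**The concern.** A site can read one section, dose accordingly, and be out of line with another. Three differences matter.

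1. A patient who clears by week 4 and is no longer clear at week 8 gets opposite instructions from the table and from Section 3.2.
2. Whether week-8 escalation is a choice or an instruction differs between sections, and within Section 3.1.2 itself.
3. The trigger differs: clearance of pustules and plaques (table), complete disease clearance (Section 3.1), persisting pustules (Section 3.1.2 text), or disease quiescence (Section 3.2), a term that is not defined.

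Weeks 8–12 come immediately before the week-12 primary assessment. Dose is also an output of the trial: Section 1.1.2 lists adequate dosing among the objectives, and Section 3.1 plans to assess the mean anakinra dose required for greatest improvement. If escalation is automatic at one site and optional at another, part of that mean reflects which section was read. Section 7.1.8 counts any departure from the protocol as a deviation, and Section 7.2.1 requires all deviations to be reported within 7 days, so the same decision may or may not be reportable.

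**Working it through.** The plan gives no figure to reproduce. The check sets the rules side by side.

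**Inputs.** Dose levels 100, 200 and 300 mg/day, with 300 limited by weight (Section 3.1.2); assessments at weeks 4 and 8, treatment ending at week 12 (Section 3.1).

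**Assumptions.** Quiescence in Section 3.2 is read as complete clearance; visits fall on their nominal days; there are no holds, reductions or postponements for adverse events.

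**Grid.** Clear or not at week 4 × clear or not at week 8 × below or above 75 kg = 2 × 2 × 2 = 8 combinations. In the four that are clear at week 8, every section leaves the dose unchanged. The other four, in mg/day for weeks 8–12:

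| Week 4 | Weight | Section 3.1 | Table in 3.1.2 | Section 3.2 | Dose meeting all three |
|---|---|---|---|---|---|
| Clear | above 75 kg | 100 or 200 | 200 | 100 | none |
| Clear | below 75 kg | 100 or 200 | 100 (no increase) | 100 | 100 |
| Not clear | above 75 kg | 200 or 300 | 300 | 300 | 300 |
| Not clear | below 75 kg | 200 | 200 (no increase) | 200 | 200 |

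One of the 8 combinations has no dose that satisfies all three. In two others (rows 2 and 3) Section 3.1 permits a choice where the other two give a single dose, but a common dose exists.

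**Size in row 1.**
- Weeks 8–12: 28 × 100 = 2,800 mg against 28 × 200 = 5,600 mg, a difference of 2,800 mg.
- Twelve weeks, Section 3.2: 84 × 100 = 8,400 mg.
- Twelve weeks, table: 56 × 100 + 28 × 200 = 11,200 mg.
- Ratio: 11,200 / 8,400 = 1.33, or 33% more.

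**Size in row 3, option declined against taken.**
- Declined: 28 × 100 + 56 × 200 = 14,000 mg.
- Taken: 28 × (100 + 200 + 300) = 16,800 mg.
- Ratio: 16,800 / 14,000 = 1.20, or 20% more.

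A patient who declines complies with Section 3.1 but departs from the table and Section 3.2.

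**Does the meaning of quiescence rescue row 1?** No. A patient left on 100 mg/day at week 4 has no week-8 step in Section 3.2 under any definition of the word.

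**Trigger.** Section 6.2.2 says "Total body surface area involvement of pustules and erythematous plaques will be measured in this study". A patient with plaques but no pustules at week 4 is to be escalated under the table, while the Section 3.1.2 text provides no escalation for that patient.

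**Weight bound.** It is above 75 kg in the précis and Section 3.2, and at least 75 kg in Section 3.1.2. The difference bites only at exactly 75 kg.

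**The case against.** The best defence is that the protocol names its governing rule. Section 3.1.2 says the table is to be followed, and Section 3.1 refers to Section 3.1.2 in its week-4 sentence, using the same dose-level term that it uses at week 8. The permissive text in Section 3.1.2 comes before the table that governs it. On this view Section 3.2 is only about administration. This carries weight, but it does not settle the matter: calendar footnote c sends staff to Section 3.2 for the escalation criteria, and Section 3.2 contradicts the table in terms.

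A second defence is that most of the differences can be reconciled. That stands. A reader might count three of the eight combinations as conflicts, because the permitted doses are not identical in three. In two of those three, following the table breaches no section. Nor is the absence of a table row for a patient below 75 kg who is not clear at week 8 a real gap: a rule that escalates only at or above a weight implies no increase below it.

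A third defence is that the effect on results is small. Clearance by week 4 followed by loss of clearance by week 8 may be uncommon, and the documents give no rate. Doses taken are recorded (Section 3.1), and the weekly team meeting (Section 7.4.1) may align practice. These points limit the consequence. They do not tell a site which instruction to follow.

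**Conclusion.** The concern holds in a limited form. There is one outright contradiction: above 75 kg, clear at week 4, not clear at week 8, where the table and Section 3.2 differ by 100 mg/day for 28 days. There is also an option-versus-directive difference, which affects compliance for patients above 75 kg not clear at both visits, and there are four wordings of the trigger. The weight bound is a minor discrepancy.

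The counts are of rule combinations, not of patients, and rest on reading quiescence as complete clearance and on nominal visit days. Section 3.1 allows one week either side of these visits, so the milligram totals are nominal.

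A reader might infer that the regimen is generally undefined for the last four weeks of treatment. The documents do not support that: in seven of the eight combinations at least one dose satisfies Section 3.1, the table and Section 3.2 together. A reader might also infer that the primary endpoint is compromised. It is not: TBSAI50 remains computable. What depends on the section followed is the regimen behind that proportion, the mean required dose, and the deviation status of some dosing decisions. The flowchart in Section 3.5 could not be read in the available text, so any week-8 wording there was not checked.

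**What to change.** In one wording amendment, reconcile Section 3.1, the text and table of Section 3.1.2, Section 3.2 and calendar footnote c so that they give:

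- one escalation trigger, with quiescence defined if the term is kept;
- one wording on whether escalation is optional or directed;
- one weight bound;
- one week-8 rule for patients clear at week 4 but not at week 8.

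Align the summaries in the précis and in Section 2.3.3, where the arm description has no weight limit. The investigators decide which rule applies; this point takes no position on that. The amendment needs no new data and no additional visits.

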3.2 DRUG ADMINISTRATION

Anakinra is supplied in single-use 1 ml prefilled glass syringes with 27 gauge needles as a sterile, clear, colorless-to-white, preservative-free solution for daily subcutaneous (SC) administration. Each 1 ml prefilled glass syringe contains: 0.67 ml (100 mg) of anakinra in a solution (pH 6.5) containing sodium citrate (1.29 mg), sodium chloride (5.48 mg), disodium EDTA (0.12 mg), and polysorbate 80 (0.70 mg) in water for injection, USP.

Patients will be instructed verbally and in writing that anakinra should be protected from light, stored in the refrigerator at 2°C to 8°C (36°F to 46°F) away from children, and never frozen. Patients will be instructed not to use any syringe if the solution appears discolored or cloudy or has been at room temperature ≥ 24 hours. Patients will be instructed to avoid shaking the pre-filled syringes, to use each syringe only once, and to inject the entire volume of solution. Patients will receive a diagram (**APPENDIX C: PATIENT HANDOUT**) of body sites where anakinra is to be injected, emphasizing the importance of avoiding veins, arteries and injecting into a new site each day. Self-injection demonstration and technique will be provided once the baseline visit has concluded.

All patients will be given a puncture-resistant container for proper disposal of syringes after use.

Abbreviated Title: Anakinra in pustular dermatoses

Version Date: December 12, 2018

All patients will initiate anakinra therapy with one 1ml (100 mg) prefilled syringe injected subcutaneously daily. Those who achieve disease quiescence on this dose by week 4 will continue at this dose until week 12.

Those who do not demonstrate disease quiescence at week 4 will increase their dose to 2-1ml prefilled syringes (total of 200 mg) to be injected subcutaneously daily. Those individuals who weight >75kg and do not demonstrate disease quiescence by week 8 on anakinra 200 mg/day will be instructed to increase their dose to 3-1ml prefilled syringes (total of 300mg) injected subcutaneously daily.

Patients who miss a dose will be instructed to administer the dose as soon as they remember. However, if it is almost time to administer the next dose, the patient will be directed to skip the missed dose and proceed with their regularly scheduled dose. Patients will be reminded to avoid double-dosing in an effort to make up the missed dose.

If a patient misses a dose of study drug, it will be recorded in the medical record and on the CRF. Missed doses will not be reported to the IRB as a protocol deviation unless the patient misses >5 doses per month.

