3.3 DOSE MODIFICATIONS

All dose modifications must be discussed with the PI. This study will utilize version 4.0 of the NCI Common Terminology Criteria for Adverse Events (CTCAE) (<http://ctep.cancer.gov/reporting/ctc.html>) for toxicity and adverse event reporting. Expected pre-existing or concurrent manifestations of inflammatory pustular dermatoses include fatigue, malaise, pain, pruritus, arthritis, enthesitis, alopecia, pustular and papular skin lesions, hypopigmentation, hyperpigmentation, skin dryness, nail changes, koebnerization at sites of trauma or injections, uveitis, conjunctivitis, rash, hypocalcemia, hypoalbuminemia and leukocytosis. Any of the above symptoms newly presenting after initiation of anakinra must be carefully evaluated for attribution, i.e., new skin rash may be biopsied to determine drug reaction versus pustular dermatosis. See **APPENDIX D: DOSE MODIFICATION FLOW CHART** for Dose Modification Flow Chart.

Adverse event	CTCAE grade/attribution	Protocol Action
Any adverse event (excluding infection, treatment-related malignancy)	Grade 2 >7 days that is probably or definitely related to anakinra.	Hold study drug; *If AE resolves to \leq grade 1 or baseline within 14 days: resume dose at same dose level. ** If AE does not resolve to \leq grade 1 or baseline within 14 days: patient comes off drug.
Any adverse event (excluding infection, treatment-related malignancy)	Same grade 2 >7 days recurs that is probably or definitely related to anakinra.	Hold study drug; *If AE resolves to \leq grade 1 or baseline within 14 days: decrease dose by 1 dose level. **If AE does NOT

Abbreviated Title: Anakinra in pustular dermatoses

Version Date: December 12, 2018

		resolve to \leq grade 1 or baseline within 14 days: patient comes off drug.
Any adverse event (excluding infection, treatment-related malignancy)	Same grade 2 >7 days recurs after dose reduction that is probably or definitely related to anakinra.	Patient comes off drug.
Any adverse event (excluding infection, treatment-related malignancy)	Grade 3 that is probably or definitely related to anakinra.	Hold study drug; *If AE resolves to \leq grade 1 or baseline within 14 days: decrease dose by 1 dose level. **If AE does NOT resolve to \leq grade 1 or baseline within 14 days: patient comes off drug.
Any adverse event (excluding infection, treatment-related malignancy)	Same grade 3 recurs after dose reduction that is probably or definitely related to anakinra.	Patient comes off drug.

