11.1.3 Formulation and preparation

Anakinra is supplied in single use prefilled glass syringes with 27 gauge needles as a sterile, clear, colorless-to-white, preservative free solution for daily subcutaneous (SC) administration. The solution may contain trace amounts of small, translucent-to-white amorphous proteinaceous particles. Each prefilled glass syringe contains: 0.67 mL (100 mg) of anakinra in a solution (pH 6.5) containing disodium EDTA (0.12 mg), sodium chloride (5.48 mg), sodium citrate (1.29 mg), and polysorbate 80 (0.70 mg) in Water for Injection, USP.

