11.1.5 Administration procedures

This medication is injected subcutaneously once a day.

Abbreviated Title: Anakinra in pustular dermatoses

Version Date: December 12, 2018

Before injecting each dose, the injection site should be cleaned with rubbing alcohol. It is important to change the location of the injection site daily. The medication should not be injected into an area that is tender, red, bruised, or hard or which has scars or stretch marks.

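### Section 3.2 tells patients to inject the whole of every 100 mg syringe, which contradicts the 50 mg daily dose at level -1 (low-severity internal inconsistency)

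*Combined protocol and SAP*

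**What the plan says.** Section 3.2 lists handling instructions given to every patient verbally and in writing. Among them, patients are told "to use each syringe only once, and to inject the entire volume of solution". The section then gives the syringe count for each planned dose. It begins "All patients will initiate anakinra therapy with one 1ml (100 mg) prefilled syringe injected subcutaneously daily" and goes on to two syringes for 200 mg and three for 300 mg. It gives no count or method for 50 mg. On training it says "Self-injection demonstration and technique will be provided once the baseline visit has concluded".

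Section 11.1.3 describes the same single-use product: "Each prefilled glass syringe contains: 0.67 mL (100 mg) of anakinra". Section 11.1.5 adds "This medication is injected subcutaneously once a day" and describes no part-syringe technique.

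In section 3.1.2, a patient whose adverse event on level 1 calls for a reduction "may be reduced to dose level -1, 50mg SC daily (see Section 3.3". The same section adds: "Patients who require dose reduction due to an adverse event at any point in this study will not be eligible for dose escalation". Section 3.3 sets out when a dose is lowered by one level and states "All dose modifications must be discussed with the PI".

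**The concern.** Level -1 is the protocol's safety dose for someone who has had a drug-related event at 100 mg. The written administration rule and the supplied syringe, taken together, cannot produce it. A patient who did exactly what section 3.2 says would go back to the dose on which the event occurred.

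Two other parts of the plan assume that the lower dose was really given. Section 3.3 takes a patient off drug if the same event returns after a reduction, which makes sense only if the dose was in fact reduced. Section 1.1.2 lists adequate dosing and safety as a secondary objective. Because section 3.1.2 bars escalation after a reduction, a patient at level -1 who stays on drug would be self-injecting 50 mg daily for the rest of treatment.

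**Working it through.** **Inputs.** Syringe content is 100 mg in 0.67 mL (sections 3.2 and 11.1.3). Dose levels are 50, 100, 200 and 300 mg daily (section 3.1.2). Dosing is once daily (sections 3.1.2 and 11.1.5). Planned size is 25 evaluable patients with a ceiling of 30 (section 8).

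**The plan's own syringe counts, whole syringes injected in full.**
- 1 × 100 = 100 mg (0.67 mL)
- 2 × 100 = 200 mg (1.34 mL)
- 3 × 100 = 300 mg (2.01 mL)

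These match section 3.2.

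**Level -1.**
- Syringes needed: 50 / 100 = 0.5, not a whole number.
- Concentration: 100 / 0.67 = 149.25 mg/mL.
- Volume for 50 mg: 50 / 149.25 = 0.335 mL, half of the 0.67 mL fill.
- Dose if the entire volume is injected: 100 mg, and 100 / 50 = 2.0 times the intended dose.
- Dose if someone takes half of the nominal 1 mL instead: 0.5 × 149.25 = 74.6 mg, also wrong.

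Giving 100 mg every other day would use whole syringes, but the stated schedule is daily.

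**Which reductions are affected.** In syringes, the three steps are 3 to 2, 2 to 1, and 1 to 0.5. Only the last fails.

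**Who can reach level -1 (section 3.3).** The event must occur on level 1, be judged probably or definitely drug-related, and follow one of these routes:
- a non-infection grade 3 event that settles to grade 1 or baseline within 14 days;
- the same grade 2 event lasting more than 7 days that recurs, and again settles within 14 days;
- a recurrent grade 2 infection, once treated and resolved.

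The exception list in section 3.3 removes many grade 2 events from these routes, including injection site reaction, skin or soft tissue infection, paronychia, fever, fatigue, headache and nausea. Related grade 3 infection and any grade 4 infection end treatment. From week 4, patients who have not cleared move to level 2, where a first reduction is to one whole syringe. After that visit, level 1 therefore holds mainly patients who have cleared.

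**Illustrative frequency.** The protocol gives none. For the injection-site route alone, section 11.1.2 reports reactions in 71% of patients, 3.2% of them severe. Assume that severe means grade 3 and that the 3.2% applies per affected patient. Then 0.71 × 0.032 = 2.3%, or 0.6 patients of 25 and 0.7 of 30. Some of these would come off drug instead, because the reactions typically last 14 to 28 days and section 3.3 allows 14. Other routes would add to this by an amount the documents do not let us estimate.

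**The case against.** The strongest reply is that the sentence in section 3.2 is general handling advice, taught when every patient is on a full syringe, while reductions are governed by sections 3.1.2 and 3.3, where 50 mg is explicit. No patient drifts into level -1. Every route to it starts with a drug hold, and every dose change is discussed with the PI. Section 4.1 has patients with adverse events contact the team at once and expect a clinic visit. Section 3.1 requires emergency evaluation for related serious events of grade 3 or above, and section 7.4.1 has the team discuss each patient weekly. Telephone calls, diaries and dose records could also reveal a wrong dose.

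Most of this stands, and it limits the weight of the point. A reader might infer that patients reduced to level -1 would in practice be restarted on 100 mg. The documents do not support that: the order is for 50 mg, and clinical contact is expected before restart. What the safeguards do not do is tell the patient how to deliver 50 mg from the supplied syringe.

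A second reply is that a method may exist elsewhere. The flow chart in Appendix D, the diary and part of the Appendix C handout cannot be read in this copy, and section 11.1 refers to the package insert for full information. This also stands, so it would be wrong to conclude that the trial has no way of giving 50 mg. If a part-syringe method is given in one of those places, the unqualified sentence in section 3.2 contradicts it. A pharmacy-prepared 50 mg dose would remove the practical conflict, but no readable text provides for one.

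**Conclusion.** The inconsistency is real and of low severity. As written, section 3.2 and level -1 cannot both be followed with the supplied syringe, and literal compliance gives 100 mg where 50 mg is ordered. One of the three reduction steps is affected, and likely zero to a few of 25 to 30 patients. That range is a judgement from the triggers and exceptions in section 3.3, since the documents give no frequency.

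The conclusion rests on the 100 mg syringe being the only presentation supplied, as sections 3.2 and 11.1.3 describe. The wording conflict is certain. Whether a method is missing altogether is not, because some materials could not be read. A reader might also suspect an effect on the response estimate or the sample size, but nothing in the documents supports one. The point deserves correction because it concerns a safety dose and the correction costs almost nothing.

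**What to change.** In section 3.2 and the written patient instructions, exempt level -1 from the entire-volume rule and give the method. Either state that 50 mg is 0.335 mL, half of the 0.67 mL fill and not half of 1 mL, with the remainder discarded, or state that the pharmacy dispenses a prepared 50 mg dose. Choose the pharmacy route if the syringe cannot be read at 0.335 mL, which the documents do not say. Check that Appendix D agrees. Re-instruct the patient at restart, and use the existing diary and dose records to confirm the dose taken.

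The cost is one sentence in each place, a short re-instruction and, if the pharmacy route is chosen, preparation for the few patients concerned. No new data field is needed.
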